8.3 Serum and Plasma Marker Studies

Sera and plasma will be collected at as per study calendar in Section 9 to identify potential therapeutic targets, biomarkers, and predictors of response and autoimmune toxicity through proteomic approaches and ctDNA isolation. Whole blood will be collected in two 10 mL Serum Separator Tube (SST tube) at the designated time points and processed using standard laboratory procedures. Using a pipette, aliquots of 1 mL of serum should be transferred to cryogenic vials and stored at -80°C.

We will also collect whole blood in two 10 mL plasma preparation tubes with EDTA (PPT, BD Vacutainer, Franklin Lakes, NJ) and gently swirl tubes to mix blood with EDTA. Within two hours of collection, the sample will be processed using standard procedures for plasma separation. Plasma will be divided into 1 mL aliquots and stored at -80°C. Pellets from this separation procedure will be washed in PBS and then divided into aliquots and also stored at -80°C.

8.4 Diagnostic Tissue Samples

Tissue, fluid, or blood may be collected from standard of care procedures used to treat or diagnoses immune related toxicities. Detailed instructions for tissue collection and shipment are provided in the procedures manual.

A Phase I/II trial of combination immunotherapy with nivolumab and a CCR2/CCR5 dual antagonist (BMS-813160) with or without GVAX following chemotherapy and radiotherapy for locally advanced pancreatic ductal adenocarcinomas (PDACs)

9. STUDY SCHEDULE

Patients will be evaluated and consented at the time of initial diagnosis of LAPC. Patients should meet all eligibility criteria and complete all screening procedures prior to starting SOC chemotherapy, however they can be enrolled up to one month after initiating SOC chemotherapy to allow for time to gather all records from outside institutions if necessary. Patients will then receive 8-16 14-day cycles of FOLFIRINOX-based chemotherapy, followed by SBRT between 2-4 weeks after completion of chemotherapy. Both chemotherapy and radiation therapy are standard therapies for LAPC, and will be administered off-trial. They will have another evaluation for eligibility to receive immunotherapy after completion SBRT at which point they will be randomized during Phase II and they will initiate Cycle 1 Day 1 of combination immunotherapy within 2 weeks of completion of SBRT. The patient will undergo Post-Immunotherapy Evaluation within one week after Cycle 1 Day 28.

Pre-surgical Study Schedule						
Procedure	Screening/ Baseline	Pre-Immunotherapy Screening (within 3 weeks prior to C1D1)	Cycle 1 Immunotherapy (within 2 weeks after completion of SBRT)			End of Cycle 1 (day before surgery or C1D28, whichever is earlier) ²⁴
			C1D1 ²	C1D2 ³	C1D15 ⁴	
Visit Window ¹ (days)			-	-	+3	-3/+14
Nivolumab (All patients)			X			
GVAX (Phase 1 and Arm B patients)				X		
BMS-813160 (All patients) ⁵			X	X	X	X
Eligibility criteria	X	X				
Randomization (Phase 2 only) ⁶		X				
Demographics	X					
Medical History ⁷	X	X				
Medications	X	X	X		X	X
Physical Exam ⁸	X	X	X			X
Vital Signs and pulse ox ⁹		X	X	X	X	X
Height ⁹		X				
Weight		X	X		X	X
Performance Status	X	X	X		X	X
EKG for PR, QRS and QTcF ¹⁰		X	X		X	X
Hematology profile ^{11, 12}	X	X	X		X	X
Chemistry profile ^{11, 13}	X	X	X		X	X
TSH ^{11, 14}		X	X			X
Serum/Urine Preg ^{11, 15}	X	X	X			
CA 19-9 ¹¹	X	X	X			X
Urinalysis and microscopic exam ^{11, 16}		X				
INR ¹¹		X				
HLA-Typing ¹¹			X			
Adverse event evaluation		X	X		X	X
Vaccine Site Assessment						X
PET-CT, CT, or MRI ¹⁷	X	X				X ¹⁸
Tumor measurements ¹⁷	X	X				X ¹⁸
Pathology Review	X	X				
Peripheral blood for research (up to 100cc) ¹⁹			X			X
Serum (20cc) ¹⁹			X			X
Plasma (20cc) ¹⁹			X			X
Archival Tissue ²⁰	X					
EUS Core Biopsy ¹⁹		X ²¹				X ²²
QoL Questionnaire ²³			X			X

In order to minimize the need for research-only in-person visits, telemedicine visits may be substituted for in-person clinical trial visits or portions of clinical trial visits where determined to be appropriate and where determined by the investigator not to increase the participants risks. Prior to initiating telemedicine for study visits the study team will explain to the participant, what a telemedicine visit entails and confirm that the study participant is in agreement and able to proceed with this method. In the event telemedicine is not deemed feasible, the study visit will proceed as an in-person visit. Telemedicine visits will be conducted using HIPAA compliant method approved by the Health System and within licensing restrictions.

A Phase I/II trial of combination immunotherapy with nivolumab and a CCR2/CCR5 dual antagonist (BMS-813160) with or without GVAX following chemotherapy and radiotherapy for locally advanced pancreatic ductal adenocarcinomas (PDACs)

Pre-surgical Study Schedule Footnotes

1. Longer delays to be approved by the IND Sponsor and Principal Investigator.
2. Cycle 1 Day 1 labs do not need to be repeated if pre-immunotherapy screening labs are done within 7 days of this treatment visit.
3. Day 2 visit and assessments are not required for Arm A or Arm C patients as they do not receive GVAX
4. Day 15 visit assessments (labs, vitals, EKG) may be done locally with information regarding AEs, medications, and performance status collected via phone call or televisit
5. Anti-CCR2/5 (BMS-813160) therapy will be continued up to the day before surgery.
6. Randomization for Phase II participants will occur after re-screening eligibility criteria has been met. Due to drug availability, patients meeting re-screening eligibility after 12/19/2022 will be assigned to Arm C (not randomized).
7. Includes history of lung disease, HIV, hepatitis B or C infection, and complete cancer history, including primary site of cancer, gross location of primary tumor, secondary sites of cancer, histology, histologic grade, date of initial diagnosis, prior cancer therapy regimens.
8. Complete physical exam will be completed at baseline; focused physical examinations will be conducted thereafter. Exams, concomitant medication, AE assessments can be made up to 3 days prior to infusion.
9. Temperature, respiration rate, blood pressure, and pulse will be taken as indicated. Pulse oximetry will be taken prior to each cycle. Nivolumab: vitals will be collected prior to and at end of the infusion (+15 min). GVAX: vitals will be collected prior to and after GVAX administration. Height from any time prior to Cycle 1 may be used.
10. QT corrected for heart rate using Fridericia's method. C1D1 EKG does not need to be repeated if Pre-Immunotherapy Screening EKG is done within 7 days of C1D1 visit.
11. Labs may be collected within a window of up to 7 days prior to dosing. Labs collected for non-dosing visits (i.e. safety labs/visits) may be collected up to 3 days prior to visit. Unexpected Grade 3 or greater laboratory abnormalities should be repeated within 24-72 hours if clinically indicated and monitored as necessary to determine if event meets toxicity criteria.
12. CBC with differential including absolute eosinophil count, absolute neutrophils, absolute lymphocytes, and platelets.
13. Albumin, alkaline phosphatase, total bilirubin, bicarbonate, BUN, calcium, chloride, creatinine, glucose, potassium, total protein, SGOT [AST], SGPT [ALT], sodium, amylase, lipase. Amylase and lipase do not need to be collected at screening prior to chemotherapy.
14. T3 and FT4 to be checked reflexively if TSH is abnormal.
15. For WOCBP. Pregnancy tests must be done within 7 days of the first treatment and then will be repeated with each subsequent therapy (collected within a window of up to 3 days prior to dosing).
16. Bilirubin, blood, glucose, ketones, leukocytes, nitrite, pH, color, protein, RBC and WBC count, and specific gravity.
17. FDG-PET-CT is preferred for baseline evaluation for SBRT planning. Radiologic evaluations (CT pancreas protocol, Chest, abdomen, and pelvis with contrast) and tumor measurements will be performed at baseline, at pre-immunotherapy screening (within 3 weeks of C1D1), and at the time of surgical evaluation (post-immunotherapy). Non-contrast CT Chest and MRI Abdomen/pelvis will be done for those with contrast allergies.
18. This standard of care imaging is part of the pre-surgical evaluation and can be done anytime between immunotherapy and planned surgery.
19. Research samples will be collected at the discretion of the PI based on availability of supplies and safety of patient and staff. See Section 8 for information on correlative studies.
20. Archival tissue from non-study biopsies may be collected at any time throughout the study.
21. Biopsy (4-6 cores) will be done during endoscopy for fiducial placement (not tied to pre-immunotherapy screening visit timing).
22. EUS Guided biopsy will be obtained for research purposes if subject is not a surgical candidate. If subject is a surgical or NanoKnife candidate, biopsy will be obtained intraoperatively during surgical resection. If metastases are noted, subjects will be offered a biopsy of metastases for research purposes.
23. QOL survey may be completed up to 3 days prior to a visit.
24. If End of Cycle 1 window overlaps with C1 D15 window, these visits may be combined.

A Phase I/II trial of combination immunotherapy with nivolumab and a CCR2/CCR5 dual antagonist (BMS-813160) with or without GVAX following chemotherapy and radiotherapy for locally advanced pancreatic ductal adenocarcinomas (PDACs)

Surgery should be scheduled to occur between five to seven weeks after completion of SBRT. If surgery is scheduled after completion of Cycle 1 (i.e. >28 days from nivolumab dosing), anti-CCR2/5 (BMS-813160) therapy will be continued up to the day before surgery. A second dose of nivolumab and GVAX will not be administered because this is not considered a new cycle. Standard surgical procedure will be determined by the operating surgeon. The surgical procedure is considered standard of care, but must be performed at Johns Hopkins Hospital.

Post-treatment biospecimens will be obtained the following ways:

- Surgical candidate found to have resectable tumor – resected specimen will be obtained intraoperatively
- Surgical candidate found to have unresectable tumor – research core biopsies will be obtained intraoperatively
- Non-surgical candidate – EUS-guided tumor biopsy
 - Note, if a patient is noted to have developed metastases that can be safely biopsied (as determined by our interventional radiology team), they will be offered biopsy of the metastases.

For those who undergo a surgery or NanoKnife procedure, immunotherapy will be initiated within 6 to 12 weeks of the procedure. For those who are not surgical candidates, the immunotherapy will not be held.

Both resected and unresected patients will receive combination immunotherapy every 28 days for a total of 4 more cycles (cycles 2-5) or until the development of metastatic disease. Patients with local progression will be allowed to continue the study treatment. Patients will be expected to be on trial for approximately 7 to 9 months if they undergo surgery, and 6 months if they do not undergo surgery.

Post-surgical (or Post-Surgical Evaluation) Study Schedule																
Procedure	Each Cycle of combination immunotherapy is 28 days												EOT ¹⁶	Safety FU ¹⁶	Clinical FU ¹⁶	Survival FU ¹⁶
	C2 D1	C2 D2 ²	C2 D15 ³	C3 D1	C3 D2 ²	C3 D15 ³	C4D1	C4 D2 ²	C4 D15 ³	C5 D1	C5 D2 ²	C5 D15 ³				
Visit Window ¹ (days)	+7		+3	+7		+3	+7		+3	+7		+3	±7	+14	±14	±14
Eligibility criteria ⁴	X															
Nivolumab (All patients)	X			X			X			X						
GVAX (Ph1, Arm B, and Arm C pts)		X			X			X			X					
BMS-813160 (Ph1, Arm A, and Arm B pts)	X	X	X	X	X	X	X	X	X	X	X	X				
Medications	X		X	X		X	X		X	X		X	X	X	X	
Physical Exam ⁵	X			X			X			X			X		X	
Vital Signs and pulse ox ⁶	X	X	X	X	X	X	X	X	X	X	X	X	X		X	
Weight	X			X			X			X			X		X	
Performance Status	X		X	X		X	X		X	X		X	X		X	
EKG for PR, QRS and QTcF ⁷	X		X	X		X	X		X	X		X	X			
Hematology profile ^{8,9}	X		X	X		X	X		X	X		X	X		X	
Chemistry profile ^{8,10}	X		X	X		X	X		X	X		X	X		X	
TSH ^{8,11}	X			X			X			X			X			
Serum/Urine Pregnancy ^{8,12}	X			X			X			X			X			
CA 19-9 ⁸	X			X			X			X			X		X	
Adverse event evaluation	X		X	X		X	X		X	X		X	X	X	X	
Vaccine Site Assessment	X			X			X			X			X			
CT or MRI ¹³	X						X						X		X	
Tumor measurements ¹³	X						X						X		X	
Peripheral blood for research (up to 100cc) ¹⁴	X												X			
Serum (20cc) ¹⁴	X												X			
Plasma (20cc) ¹⁴	X												X			
QoL Questionnaire ¹⁵	X						X						X		X	
Survival Follow-up																X

A Phase I/II trial of combination immunotherapy with nivolumab and a CCR2/CCR5 dual antagonist (BMS-813160) with or without GVAX following chemotherapy and radiotherapy for locally advanced pancreatic ductal adenocarcinomas (PDACs)

In order to minimize the need for research-only in-person visits, telemedicine visits may be substituted for in-person clinical trial visits or portions of clinical trial visits where determined to be appropriate and where determined by the investigator not to increase the participants risks. Prior to initiating telemedicine for study visits the study team will explain to the participant, what a telemedicine visit entails and confirm that the study participant is in agreement and able to proceed with this method. In the event telemedicine is not deemed feasible, the study visit will proceed as an in-person visit. Telemedicine visits will be conducted using HIPAA compliant method approved by the Health System and within licensing restrictions.

Phase I and Phase II Arm B Schedule - Post-surgical Study Schedule Footnotes

1. Longer delays to be approved by the IND Sponsor and Principal Investigator.
2. Day 2 visit and assessments are not required for Arm A patients as they do not receive GVAX
3. Day 15 visit assessments (labs, vitals, EKG) may be done locally with information regarding AEs, medications, and performance status collected via phone call or televisit
4. Patients who are deemed unresectable due to local progression (i.e. without metastatic disease) may continue directly to Cycle 2 immunotherapy without rescreening. No eligibility checklist is necessary for these patients.
5. Complete physical exam will be completed at baseline; focused physical examinations will be conducted thereafter. Exams, concomitant medication, AE assessments can be made up to 3 days prior to infusion.
6. Temperature, respiration rate, blood pressure, and pulse should be taken at baseline, prior to nivolumab infusion, and at the end of the infusion. Pulse oximetry should be taken at baseline and prior to each nivolumab infusion.
7. QT corrected for heart rate using Fridericia's method. C2D1 EKG may be done up to 7 days prior to visit.
8. Labs and QOL survey may be collected within a window of up to 7 days prior to dosing. Labs collected for non-dosing visits (i.e. safety labs/visits) may be collected up to 3 days prior to visit. Unexpected Grade 3 or greater laboratory abnormalities should be repeated within 24-72 hours if clinically indicated and monitored as necessary to determine if event meets toxicity criteria.
9. CBC with differential including absolute eosinophil count, absolute neutrophils, absolute lymphocytes, and platelets.
10. Albumin, alkaline phosphatase, total bilirubin, bicarbonate, BUN, calcium, chloride, creatinine, glucose, potassium, total protein, SGOT [AST], SGPT [ALT], sodium, amylase, lipase.
11. T3 and FT4 to be checked reflexively if TSH is abnormal.
12. For WOCBP. Pregnancy tests must be done within 7 days of the first treatment and then will be repeated with each subsequent therapy (collected within a window of up to 3 days prior to dosing).
13. CT pancreas protocol: Chest, abdomen, and pelvis with contrast. Noncontrast CT Chest and MRI Abdomen/pelvis will be done for those with contrast allergies. Imaging may be performed up to 2 weeks prior to Cycle 2 Day 1 visit and up to 1 week prior to all subsequent treatment visits.
14. Research samples will be collected at the discretion of the PI based on availability of supplies and safety of patient and staff. See Section 8 for information on correlative studies.
15. QOL survey may be completed up to 3 days prior to visit. QOL survey should be attempted at EOT visit, but is not required.
16. These visits are for those patients NOT enrolling in the Maintenance Treatment Phase. The End of Treatment, Safety and Clinical Follow-up visits do not need to be completed for patients who did not receive study drug. Instead these patients will be followed every 12 weeks for information regarding future treatments, progression and survival. The End of Treatment scan does not need to be repeated if one has been performed within 6 weeks. See sections 4.10 - 4.11 for additional information. For patients continuing on Maintenance Treatment, see calendars below.

A Phase I/II trial of combination immunotherapy with nivolumab and a CCR2/CCR5 dual antagonist (BMS-813160) with or without GVAX following chemotherapy and radiotherapy for locally advanced pancreatic ductal adenocarcinomas (PDACs)

Following the 5th cycle of immunotherapy, if the patient remains free of metastatic disease, they will have the option to receive six additional 28-day cycles of maintenance immunotherapy, lasting a total of 24 weeks.

Maintenance Treatment Schedule											
Procedure	Each Maintenance Cycle is 28 days							EOT ¹⁴	Safety FU ¹⁴	Clinical FU ¹⁴	Survival FU ¹⁴
	C6D1	C6D2 ²	C7D1	C8D1	C9D1	C10D1	C11D1				
Visit Window ¹	-1/+7		-1/+7	-1/+7	-1/+7	-1/+7	-1/+7	-1/+7			
Nivolumab (All patients)	X		X	X	X	X	X				
GVAX (Ph1, Arm B, and Arm C pts)		X									
BMS-813160 (Ph1, Arm A, and Arm B pts)	X	X	X	X	X	X	X				
Medications								X	X	X	
Physical Exam ³	X		X	X	X	X	X	X		X	
Vital Signs and pulse ox ⁴	X	X	X	X	X	X	X	X		X	
Weight	X		X	X	X	X	X	X		X	
Performance Status	X		X	X	X	X	X	X		X	
EKG for PR, QRS and QTcF ⁵	X		X	X	X	X	X	X			
Hematology profile ^{6,7}	X		X	X	X	X	X	X		X	
Chemistry profile ^{6,8}	X		X	X	X	X	X	X		X	
TSH ^{6,9}	X		X	X	X	X	X	X			
Serum or Urine Pregnancy ^{6,10}	X		X	X	X	X	X	X			
CA 19-9 ⁶	X		X	X	X	X	X	X		X	
Adverse event evaluation	X		X	X	X	X	X	X	X	X	
Vaccine Site Assessment	X							X			
CT or MRI ¹¹	X				X			X		X	
Tumor measurements ¹¹	X				X			X		X	
Peripheral blood for research (up to 100cc) ¹²								X			
Serum (20cc) ¹²								X			
Plasma (20cc) ¹²								X			
Quality of Life Questionnaire ¹³	X				X			X		X	
Survival Follow-Up											X

A Phase I/II trial of combination immunotherapy with nivolumab and a CCR2/CCR5 dual antagonist (BMS-813160) with or without GVAX following chemotherapy and radiotherapy for locally advanced pancreatic ductal adenocarcinomas (PDACs)

In order to minimize the need for research-only in-person visits, telemedicine visits may be substituted for in-person clinical trial visits or portions of clinical trial visits where determined to be appropriate and where determined by the investigator not to increase the participants risks. Prior to initiating telemedicine for study visits the study team will explain to the participant, what a telemedicine visit entails and confirm that the study participant is in agreement and able to proceed with this method. In the event telemedicine is not deemed feasible, the study visit will proceed as an in-person visit. Telemedicine visits will be conducted using HIPAA compliant method approved by the Health System and within licensing restrictions.

Phase I and Phase II Arm B Schedule – Maintenance Treatment Schedule Footnotes

1. Longer delays to be approved by the IND Sponsor and Principal Investigator.
2. Day 2 visit and assessments are not required for Arm A patients as they do not receive GVAX
3. Focused physical examinations. Exams, concomitant medication, AE assessments can be made up to 3 days prior to infusion.
4. Temperature, respiration rate, blood pressure, and pulse will be taken as indicated. Pulse oximetry will be taken at baseline and prior to each cycle.
Nivolumab: vitals will be collected prior to and at end of the infusion (+15 min). GVAX: vitals will be collected prior to and after GVAX administration.
5. QT corrected for heart rate using Fridericia's method.
6. Labs and QOL survey may be collected within a window of up to 7 days prior to dosing. Labs collected for non-dosing visits (i.e. safety labs/visits) may be collected up to 3 days prior to visit. Unexpected Grade 3 or greater laboratory abnormalities should be repeated within 24-72 hours if clinically indicated and monitored as necessary to determine if event meets toxicity criteria.
7. CBC with differential including absolute eosinophil count, absolute neutrophils, absolute lymphocytes, and platelets.
8. Albumin, alkaline phosphatase, total bilirubin, bicarbonate, BUN, calcium, chloride, creatinine, glucose, potassium, total protein, SGOT [AST], SGPT [ALT], sodium, lipase, amylase.
9. T3 and FT4 to be checked reflexively if TSH is abnormal.
10. For WOCBP. Pregnancy tests must be done within 7 days of the first treatment and then will be repeated with each subsequent therapy (collected within a window of up to 3 days prior to dosing).
11. CT Chest, abdomen, pelvis (pancreas protocol) with contrast or non-contrast CT chest and MRI abdomen, pelvis for those with contrast allergies. Imaging can be done up to 1 week before each treatment visit.
12. Research samples will be collected at the discretion of the PI based on availability of supplies and safety of patient and staff. See Section 8 for information on correlative studies.
13. QOL survey may be completed up to 3 days prior to visit. QOL survey should be attempted at EOT visit, but is not required.
14. See section 4.10 – 4.11. The End of Treatment scan does not need to be repeated if one has been performed within 6 weeks

A Phase I/II trial of combination immunotherapy with nivolumab and a CCR2/CCR5 dual antagonist (BMS-813160) with or without GVAX following chemotherapy and radiotherapy for locally advanced pancreatic ductal adenocarcinomas (PDACs)

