After completion of SBRT, the patients will then be re-evaluated for eligibility for continuation in the study and must have LAPC based on NCCN Guidelines as determined by review of CT, PET, or MRI imaging at our institution. Patients who have developed metastatic disease are no longer eligible to continue in the study. If the patients remain eligible for continuation in the study after rescreening, they will be assigned or randomized to a study arm (depending on when they were enrolled).

Due to availability of BMS-813160, study enrollment was closed as of December 19, 2022. Patients randomized prior to this will continue receiving study treatment as planned until drug supply expires on July 31, 2023, then will continue to receive any remaining study cycles without BMS-813160. Any patients who were enrolled but not randomized prior to December 19, 2022 (i.e. those receiving chemotherapy) will be assigned to a new arm (Arm C).

In phase I, the combination immunotherapy consists of nivolumab, CCR2/CCR5 dual-antagonist (BMS-813160) and GVAX. In phase II, the first 10 patients will be randomized 1:1 between Arm A and Arm B. Remaining patients will be assigned to Arm C.

Arm A subjects receive nivolumab and BMS-813160, Arm B subjects receive nivolumab, BMS-813160, and GVAX, and Arm C patients will receive nivolumab and BMS-813160 for Cycle 1 (prior to surgery) and then nivolumab and GVAX for Cycles 2 and beyond.

After randomization or assignment to a study arm, subject will receive Cycle 1 of the combination immunotherapy. Cycle 1 lasts 28 days and will start within two weeks of completion of SBRT.

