8.2 Peripheral Blood Lymphocytes (PBLs) and Circulating Tumor Cells (CTC)

Whole blood of up to 100 mL will be collected as per the study calendar (Section 9) and used for PBL processing. During the Post-Immunotherapy Evaluation visit (Cycle 1 Day 28), additional plasma will be isolated from a portion of this sample (approximately 50 mL) while it is being processed for PBL to support the isolation of tumor infiltrating lymphocytes. Post-treatment expression of PD-1 and other lymphocyte activation markers will be measured and correlated with OS and MFS. PBL are isolated and stored frozen until use. PBL will be banked for measuring peripheral mesothelin-specific T-cell responses as an established parameter of immune response to treatment with GVAX. PBL will also be banked for an ELISPOT-based approach similar to the approach we used to define the mesothelin T-cell epitopes to validate mutant neoepitopes predicted for HLA-A1 and HLA-A2, including the HLA-A2-binding neoepitopes for the common Kras exon 12 mutations (KrasG12V and G12D).

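### The End of Cycle 1 collection is anchored before surgery in the schedule table, but the Section 9 text, Section 8.2 and the table's uncapped +14-day window all allow it after the operation

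*Combined protocol and SAP*

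**What the plan says.** Three places in the protocol time the same post-Cycle 1 visit.

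- **Section 9, opening text:** "The patient will undergo Post-Immunotherapy Evaluation within one week after Cycle 1 Day 28". Surgery is not mentioned.
- **Section 8.2:** "During the Post-Immunotherapy Evaluation visit (Cycle 1 Day 28), additional plasma will be isolated from a portion of this sample". The stated purpose of that plasma is to help isolate tumor-infiltrating lymphocytes. Surgery is again not mentioned.
- **Section 9, pre-surgical schedule table:** the column is headed "End of Cycle 1 (day before surgery or C1D28, whichever is earlier", with a visit window of -3/+14 days. It holds the research blood, serum, plasma, CA 19-9 and the quality-of-life questionnaire.

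The start of Cycle 1 and the operation are both timed from the end of SBRT. Section 1.7 says "Cycle 1 lasts 28 days and will start within two weeks of completion of SBRT", and Section 9 gives the same limit. For the operation, Section 9 says "Surgery should be scheduled to occur between five to seven weeks after completion of SBRT".

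Some items in the table are tied to surgery by footnote. Footnote 5 ends BMS-813160 the day before the operation. Footnote 18 says of the scan: "This standard of care imaging is part of the pre-surgical evaluation and can be done anytime between immunotherapy and planned surgery". Footnote 22 has tissue from surgical candidates taken during the operation. Footnotes 11 and 23 let laboratory samples and questionnaires be taken up to 3 days before a visit. No footnote closes the +14 days at surgery for blood, CA 19-9 or quality of life.

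**The concern.** The text and the table cannot both be followed when surgery comes early. Followed literally, the text then yields a sample labelled post-immunotherapy that was drawn after a pancreatic operation. The table's window permits the same thing over a wider range of surgery dates.

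Four consequences would follow for an operated patient sampled late:

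- The change in CA 19-9, circulating markers or lymphocytes since C1D1 would include the effect of the operation. So would quality of life, since the questionnaire mostly asks about the past week.
- The sample would also be off BMS-813160.
- The value could not be replaced. The next research blood, CA 19-9 and questionnaire are at C2D1, which for operated patients is 6 to 12 weeks after the procedure.
- The plasma could arrive too late for its stated use, because Section 8.1 has lymphocytes isolated fresh from the resected tumor.

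Section 12.7 plans paired tests of quality of life before and after treatment. Section 12.8 plans paired tests, mixed models and marker-outcome regressions. Section 8.2 plans to correlate post-treatment lymphocyte markers with OS and MFS. Only operated patients can be sampled after an operation, so late samples would tie marker values to whether surgery took place.

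**Working it through.** No figure in the plan needs reproducing; the check is calendar arithmetic. It assumes that the Post-Immunotherapy Evaluation and End of Cycle 1 are one visit, since the table has only one column after C1D15.

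**Inputs** (end of SBRT = day 0)

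- C1D1 on day s, from 0 to 14 (Sections 1.7 and 9)
- Surgery on day t, from 35 to 49, that is 5 to 7 weeks (Section 9)
- Text window: C1 Day 28 to Day 35 (Section 9)
- Table window: nominal day -3 to nominal day +14, where the nominal day is the earlier of C1D28 and the eve of surgery (Section 9)

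**Surgery in cycle days:** S = t - s + 1

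- Earliest: 35 - 14 + 1 = Day 22
- Latest: 49 - 0 + 1 = Day 50 (Day 49 if Cycle 1 starts at least one day after SBRT ends)
- Possible days: 50 - 22 + 1 = 29

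**Table window:** nominal = min(S - 1, 28), last day = nominal + 14

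- S = 22 to 29: last day = (S - 1) + 14 = S + 13
- S = 30 or later: last day = 28 + 14 = Day 42

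**Both windows against surgery**

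| Surgery (C1 Day) | Text window, Day 28-35 | Last day of table window |
|---|---|---|
| 22-27 | wholly after surgery | 13 days after surgery |
| 28 | opens on the day of surgery | 13 days after |
| 29 | runs to 6 days after | 13 days after |
| 30-34 | runs to 5 down to 1 days after | 12 down to 8 days after |
| 35 | ends on the day of surgery | 7 days after |
| 36-41 | closes before surgery | 6 down to 1 days after |
| 42 | closes before surgery | day of surgery |
| 43-50 | closes before surgery | 1 to 8 days before |

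**Counts of surgery days**

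- Text window wholly after surgery: Day 22-27, 6 of 29
- Text window with at least one post-operative day: Day 22-34, 13 of 29
- Table window with at least one post-operative day: Day 22-41, 20 of 29

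**Consistency check.** With surgery on Day 22 the table window opens on Day 21 - 3 = 18, which is the last day of the C1D15 +3 window. Footnote 24 provides for this: "If End of Cycle 1 window overlaps with C1 D15 window, these visits may be combined". The authors therefore did foresee surgery this early.

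**Would a cap work?** If collection ends the day before surgery and the -3 limit stays, the window runs from S - 4 to S - 1, which is 4 days, for S = 22 to 29. It then widens by a day at a time to 18 days (Day 25-42) for S = 43 or later. Every permitted surgery date keeps a usable pre-operative window.

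**The case against.** The strongest reply is that the documents already mean this visit to be pre-operative. The table is titled as pre-surgical and its nominal day always precedes the operation. BMS-813160 is marked as still being taken in that column. The column's scan belongs to the pre-surgical work-up, and footnote 24 brings the visit forward when surgery is early. On that reading the +14 days serve unoperated patients and those with late surgery, and what is left is stale text and a missing clause. This stands as to intent. It does not remove the conflict: the text gives a different rule, and no footnote limits the window for the items at issue.

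Three stronger readings are tempting, and the documents do not support them.

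- *Most operated patients will be sampled after surgery.* If start and surgery dates were independent and uniform over whole days, the table window would pass surgery in 180 of 225 combinations (80%). The protocol gives no basis for that timing. The figure also counts any window with one post-operative day, although the nominal day is always before surgery. It does not describe when samples are taken.
- *The exploratory results are confounded.* They could be, if late collection occurred. Nothing in the documents shows that it did, and collection and surgery dates would reveal it.
- *The primary endpoint is at risk.* Tissue for the immune response is taken during the operation or by EUS-guided biopsy, and imaging is limited to the period before surgery.

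It is also fair to say that schedule edits now reach few patients. Section 1.7 closed enrollment on December 19, 2022, and Section 12.2 anticipates 3 to 5 patients in Arm C. At the protocol's estimated 30-40% resected, that is 0.3 x 3 = 0.9 to 0.4 x 5 = 2.0 resections. This is why the analysis rule matters more than the schedule wording.

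**Conclusion.** The point holds as an internal inconsistency with a limited statistical consequence. The text and Section 8.2 ignore surgery, the table's anchor respects it, and the table's window is open past it. For surgery on Day 22-27, the text rule puts the only planned post-Cycle 1, pre-operative collection wholly after the operation. The table permits post-operative collection for surgery on Day 22-41 and excludes it from Day 43.

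The exposure is confined to operated patients and to exploratory analyses. Section 12.2 allows at most 12 + 15 = 27 treated patients. At 30-40% resected, that is 27 x 0.3 = 8.1 to 27 x 0.4 = 10.8, or about 8 to 11 resections. Patients explored but not resected, or treated by NanoKnife, would be additional, and the documents give no figure for them. Section 12.2 expects only about 10 patients per group, so even a few mistimed values could shift a paired comparison.

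The conclusion rests on the stated SBRT-based limits being followed, on the two visit names meaning one visit, and on counting the text window from Day 28 itself. It should be corrected, but it does not threaten the primary objective.

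**What to change.** 1. **Section 9 text and Section 8.2:** replace the bare Day 28 timing with a reference to the End of Cycle 1 definition in the table.
2. **End of Cycle 1 column:** keep -3/+14, and add for research blood, serum, plasma, CA 19-9 and quality of life: *and no later than the day before surgery*.
3. **Sections 12.7 and 12.8:** state that any sample or questionnaire dated on or after surgery is not used as the post-Cycle 1 time point and is listed separately. This also covers patients whose visits are already complete, and it needs only the collection and surgery dates.

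No visit or sample is added. The cost is slightly less scheduling freedom in operated patients and possibly a few missing post-Cycle 1 values. A sample drawn on the day of surgery but before the operation would be among those set aside.
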